**Table 8-1. Definition of Responses Categories**

| Category                | Definition  |
|-------------------------|---|
| Complete Remission (CR) | 
 
Documented “complete remission” or “complete response” or “No evidence of disease” in the EHR and
 
All peripheral blooda (within a 2-week period before or after the date of BM biopsy) and BM indices meeting the threshold for CR as defined in the IWG 2006 MDS response criteria and
 
All peripheral blood resultsa and the corresponding BM biopsy completed within a 4-week period before or after the CR documentation date
 
Cases that have the required peripheral blood and BM indices meeting the threshold for CR as defined in the IWG 2006 MDS response criteria but lack EHR documentation of CR will be adjudicated by an independent assessor
 
  |
| Real-world CR (rw-CR)   | 
 
EHR documentation of CR (as above) with or without all corresponding IWG 2006 indices; partial availability of indices will also fall into this category
 
  |
| Partial Remission (PR)  | 
 
Documented “partial remission” or “partial response” or “improved disease” or “responding disease” or similar termsb in the EHR and
 
All peripheral blooda (within a 2-week period before or after the date of BM biopsy) and BM indices meeting the threshold for PR as defined in the IWG 2006 MDS response criteria and
 
All peripheral blood resultsa and the corresponding BM biopsy completed within a 4-week period before or after the PR documentation date
 
Cases that have the required peripheral blood and BM indices meeting the threshold for PR as defined in the IWG 2006 MDS response criteria but lack EHR documentation of PR will be adjudicated by an independent assessor
 
 |

| Category   | Definition  |
|--|---|
| Real-world PR (rw-PR)  | 
 
EHR documentation of PR (as above) with or without all corresponding IWG 2006 indices; partial availability of indices will also fall into this category
 
  |
| Marrow CR (mCR)  | 
 
Based on BM blast count, without requirement of EHR documentation
 
BM: <math>\leq 5\%</math> myeloblasts and decrease by <math>\geq 50\%</math> over pretreatment count
 
   |

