### 8.7.1. Analysis Sets

The Full Analysis Set (FAS) will include all enrolled patients who took at least 1 dose of AZA.

The Effectiveness Evaluable Analysis Set (EEAS) will include all FAS patients who had at least one response assessment or with a documented death after the index date.

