### 8.7.4. Effectiveness Analyses

For the primary effectiveness analysis, CR rates will be evaluated using the FAS. The point estimate and the corresponding 95% CIs based on the Clopper-Pearson exact method will be provided. The same method will be applied to rw-CR, ORR, and rw-ORR using the FAS.

The time-to-event effectiveness endpoints including PFS, DCR, rw-DCR, DOR, rw-DOR, TTNT, and OS will be analyzed using the Kaplan-Meier method. Kaplan-Meier curves will be provided for the time-to-event endpoints. The endpoints of PFS, TTNT, and OS will use FAS. DCR and rw-DCR will include the FAS patients who achieve a CR or rw-CR, respectively. DOR and rw-DOR will include the FAS patients who achieve an OR or rw-OR, respectively.

CCI

Sensitivity analyses will be performed for the primary and secondary endpoints (except DCR, rw-DCR, DOR, and rw-DOR) using EEAS.

The results of this study will be compared to the ongoing Phase 1b single -arm study of magrolimab + AZA (Study 5F9005) in patients with untreated higher-risk MDS. A detailed statistical analysis for comparison will be described in the statistical analysis plan.

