managing patients in clinical practice rather than for research purposes. This may impede the standardization of the data collection methods and instruments and the reporting practices of the physician. Secondly, RWD databases are subject to coding errors. Problems with inadequate or inaccurate codes in the databases may introduce some level of misclassification bias in the study. Likewise, some variables of interest may not be as complete across the entire study population. Thirdly, each database has a close link to a dedicated network (McKesson Life Sciences USON) and, therefore, contains information on patients only when they are seen by physicians within that network. As such, services and procedures provided outside of the network (eg, emergency hospitalizations) are not captured by the database, including drugs received by patients from pharmacies not affiliated with the same network.

Misclassification of primary endpoints will be mitigated by use of complete ascertainment of all IWG response criteria and independent adjudication by a qualified hematologist employed by McKesson with no direct Gilead involvement.

Patient treatment history prior to the first encounter at a practice within the network may only be available in physician progress notes and may not be well captured or only partially captured in the EHR. Similarly, oral therapies are recorded in or prescribed through EHR-related systems, but fulfillment is not observable. In this study, attempts will be made to confirm receipt of oral therapies through chart review to help mitigate this potential limitation.

Death data are relatively complete. The primary source of death information will be structured and unstructured records of death in the iKM EHR database. McKesson has certification to access the LADMF of the Social Security Administration and, as such, this will be a supplementary source of vital (death) records in addition to the NDI of the Centers for Disease Control. Common patient identifiers (patient ID, name, and birth date) will be used to link patients from the iKM data warehouse and iKM chart review. The social security number (SSN) will be used to link patients from iKM and LADMF data sources. All patients within iKM are assigned a unique patient identifier by iKM version (eg, some large practices have separate installations by location). When linking to the LADMF, patient SSN is used. Some practices do not collect SSN and some patients may not report it.

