Death information is updated weekly in the LADMF and is as current as it is reported to the Social Security Administration. However, death dates recorded in the LADMF are not complete due to limitations on access to records for research purposes {Navar 2019}. LADMF and hospital death records were compared after access restrictions imposed in 2011 {Levin 2019}. After 2011, LADMF sensitivity for in-hospital deaths was 14.8% (compared with 88.9% before 2011) and 28.9% for out-of-hospital deaths (compared with 71.4% before 2011). The LADMF specificity, however, was greater than 99% both prior to and after 2011. Peters and colleagues (2017) compared capture of death dates in the LADMF with a multi-phased approach that assessed online databases (including LADMF), EHR records, and provider follow-up {Peterss 2017}. The authors reported that 42.7% of death records were identified by the LADMF, and the remainder were identified from another online database (32.6%), EHR records (22.2%), and provider follow-up (3.5%). Overall, the sensitivity was 58.5%, with 100% specificity.

In a study of the iKM EHR database and LADMF, it was observed that 93.3% of all death records were captured in structured fields and 6.7% of death records were solely identified by the LADMF. Among deaths recorded by both structured data and the LADMF, concordance was 88.0%. When both structured and unstructured data are available, 99.4% of death records are captured from these sources, with 0.6% of death records solely identified by the LADMF. Between 2015 and 2019, the proportion of death records captured by structured data trended upward (slope = 4.04).

Based on previous studies of other solid tumors, it is estimated that physician-assessed response will be available for greater than 60% of patients in the RWD. However, this may be impacted by BM reports and may vary considerably for patients with MDS. In standard clinical practice in the treatment of MDS, bone marrow biopsies are not routinely performed other than during diagnosis and at suspected disease progression. If BM biopsy results are unavailable for a significant proportion of patients, this will lead to an underestimate of the CR and PR rate (as defined in the Table 8-1) in the study. Therefore, the interpretation of data collected and analysed retrospectively will be dependent on the completeness and quality of the data.

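### Patients without an on-treatment marrow count as non-responders for CR, the one named sensitivity set (EEAS) does not require a marrow, and the exact interval may therefore miss the true rate

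*Protocol*

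**What the plan says.** **Numerator.** Table 8-1 requires blood and "BM indices meeting the threshold for CR as defined in the IWG 2006 MDS response criteria", with blood counts within 2 weeks of the marrow and both within 4 weeks of the documented response. Cases that meet the indices but lack a chart note go to an independent assessor. That route still needs the marrow.

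**Denominator.** Section 8.7.1: "The Full Analysis Set (FAS) will include all enrolled patients who took at least 1 dose of AZA". Section 8.7.4: "For the primary effectiveness analysis, CR rates will be evaluated using the FAS". On the interval: "The point estimate and the corresponding 95% CIs based on the Clopper-Pearson exact method will be provided".

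**Sensitivity analysis.** Section 8.7.4: "Sensitivity analyses will be performed for the primary and secondary endpoints (except DCR, rw-DCR, DOR, and rw-DOR) using EEAS". Section 8.7.1 defines the EEAS as "all FAS patients who had at least one response assessment or with a documented death after the index date".

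**Limitations.** Section 8.10 says that in routine MDS care marrows are seldom done except at diagnosis and at suspected progression, and then: "If BM biopsy results are unavailable for a significant proportion of patients, this will lead to an underestimate of the CR and PR rate". Earlier in the same section, misclassification of the primary endpoints is said to be mitigated by "use of complete ascertainment of all IWG response criteria", together with independent adjudication.

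**Use of the result.** Sections 6.1 and 8.7.4 say the results will be set against the single-arm Study 5F9005 to judge what magrolimab adds to azacitidine.

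**The concern.** A patient who is never sampled on treatment stays in the denominator and cannot enter the numerator. If marrows are done mainly at suspected progression, patients who are doing well are the ones least likely to have one, so true CRs are lost.

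A sensitivity analysis should vary the assumption in doubt, which here is marrow availability. The EEAS varies something else. A response note does not imply a marrow, and a death qualifies a patient with no assessment at all.

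Study size is justified in Section 8.5 by interval width alone. A narrow interval around a rate that is too low says nothing about this bias. Because the azacitidine rate is the external comparator, a shortfall in it would be read as benefit from magrolimab.

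**Working it through.** **Inputs from the protocol.** About 400 patients; planning range for CR 5% to 25% (Section 8.5); Clopper-Pearson 95% interval (Section 8.7.4); overall survival of about 13 months (Section 6.1); index dates from 2014 to 1 January 2020, with data collected to 1 January 2021 (Section 8.2).

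**Input not in the protocol.** m, the share of true CRs that have a usable marrow. It is assumed over a range. The figure above 60% in Section 8.10 is physician-assessed response in solid tumours and cannot stand in for m.

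**Step 1: reproduce the plan's figures.** For x responders of n, the limits are the 2.5% quantile of Beta(x, n − x + 1) and the 97.5% quantile of Beta(x + 1, n − x). For 60/400 this gives 15.0% (11.6, 18.9), as in Table 8-5. All 25 cells reproduce to 0.1 point (responder counts rounded up where needed). At a 25% rate the width is 10.07 points at n = 301 and at most 10.0 from n = 305, so the stated width holds to rounding. The table is correct as sampling error.

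**Step 2: expected observed rate.** With true rate p, the expected FAS rate is q = p × m and the shortfall is p × (1 − m). For p = 15% and m = 0.8, q = 12.0% and the shortfall is 3.0 points. For m = 0.6, q = 9.0% and the shortfall is 6.0 points.

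**Step 3: coverage.** Sum the Binomial(400, q) probabilities over every x whose exact interval contains p. For p = 15%:

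| m | Expected rate | 95% CI at expected count | Coverage of 15% |
|---|---|---|---|
| 0.9 | 13.5% | 10.3, 17.2 | 89% |
| 0.8 | 12.0% | 9.0, 15.6 | 64% |
| 0.7 | 10.5% | 7.7, 13.9 | 28% |
| 0.6 | 9.0% | 6.4, 12.2 | 5% |
| 0.5 | 7.5% | 5.1, 10.5 | 0.3% |

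Across true rates of 5% to 25%, coverage is 94% down to 81% at m = 0.9, and 88% down to 37% at m = 0.8. The interval at the expected count excludes the true rate once m is at or below about 0.55, 0.70, 0.75, 0.80 and 0.82 for true rates of 5%, 10%, 15%, 20% and 25%.

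**Step 4: what the EEAS would show.** Assume exponential survival with median 13 months (hazard λ = ln 2 / 13), uniform entry and follow-up of 12 to 84 months. The expected share dead by cutoff is 1 − (e^(−12λ) − e^(−84λ)) / (72λ) = 0.866. If 60% of the rest have a response assessment, the EEAS share is 0.866 + 0.134 × 0.6 = 0.946, or about 378 of 400. With p = 15% and m = 0.5 there are 400 × 0.15 × 0.5 = 30 observed CRs:

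- FAS: 30/400 = 7.5% (5.1, 10.5)
- EEAS: 30/378 = 7.9% (5.4, 11.1)

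The two agree closely and both exclude 15%. If the EEAS held only 240 patients, it would give 30/240 = 12.5% (8.6, 17.4): still low, though that interval includes 15%.

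**Step 5: a marrow-evaluable set.** If half of all patients had a marrow and having one were unrelated to response, the result would be 30/200 = 15.0% (10.4, 20.7). Section 8.10 gives reason to doubt that independence, so this is a second reading and not a correction.

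**The case against.** The strongest replies are these.

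- **The bias is disclosed and the convention is recognised.** Counting missing as non-response in a full analysis set is ordinary, and Section 8.10 states the consequence. This stands, but disclosure does not size the bias.
- **The protocol has partial gauges.** rw-CR is analysed on the same FAS with the same exact method and drops the marrow requirement. Stage 1 reports completeness and allows the protocol to be modified. A reader might infer that the shortfall is never measured; the documents do not support that. The gauges are nevertheless indirect. rw-CR can include unconfirmed CRs and misses responders with neither a note nor a marrow. Stage 1 reviews about 20 charts and sets no marrow threshold.
- **The SAP may add analyses.** It is not shown, and the Study 5F9005 comparison is deferred to it. The point is therefore confined to what the protocol fixes: the primary set, the named sensitivity set, and the statement about ascertainment.
- **The ascertainment wording may mean something narrower.** It can be read as abstracting and adjudicating every IWG component found in the chart, while the later paragraph concerns marrows never done. On that reading it is loose wording and not a proven contradiction, but it still needs clarifying.
- **Error is not purely one-directional.** The Table 8-1 footnote sets missing peripheral blasts to 0%, which can inflate CR. This stands, so the FAS rate is not a strict lower bound.

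**Conclusion.** The point holds in a conditional form. By construction the primary CR rate is pulled down by the share of true CRs that lack a qualifying marrow, the EEAS as defined does not address this, and the exact interval carries sampling error only.

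A reader might go further and conclude that the interval will exclude the true rate. That does not follow. At m = 0.9 the interval at the expected count includes the true rate at every planning value, and at m = 0.8 it still does for true rates of 5% to 15%. The supportable statement is that it may exclude the true rate, and that this becomes likely once m falls to roughly 0.55 to 0.82, depending on the true rate.

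The size rests on m, which the protocol does not give, and on 400 patients. The EEAS illustration also rests on the assumed survival, entry and assessment pattern. The expected direction, through missing marrows, is the sponsor's own and favours the combination in the comparison with Study 5F9005.

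**What to change.** 1. In Sections 8.7.1 and 8.7.4, report the number and share of FAS patients with at least one post-index marrow and the required blood counts in the Table 8-1 window, before next MDS treatment.
2. Add a sensitivity analysis of CR and PR in that marrow-evaluable set, shown beside FAS CR and rw-CR. Leave ORR out, because hematologic improvement counts towards ORR and needs no marrow. State that FAS CR is expected to be understated through missing marrows, without calling it a strict bound. State also that the marrow-evaluable set is smaller and selected, since marrows are done mainly at suspected progression, and so does not replace the FAS estimate. Weighting by baseline covariates is optional and does not remove selection by on-treatment status.
3. Carry these results into the Study 5F9005 comparison.
4. Reconcile "use of complete ascertainment of all IWG response criteria" with the later paragraph of Section 8.10, for example by limiting it to full abstraction of the IWG components available in the chart.

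The cost is low: Table 8-4 already lists on-treatment marrow blasts and blood counts for collection. The price is a wider interval in a selected subset, and a range of estimates to interpret in place of one figure.

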#### **8.10.1. Joint RWD Partner/Gilead Responsibilities**

##### **8.10.1.1. Quality Control of Data**

McKesson Health Sciences is responsible for review of the data collected throughout the study to verify adherence to the protocol and the completeness, consistency, and accuracy of the data being entered on the forms. However, secondary reconciliation and data quality check will be performed by Gilead personnel. The service agreement between Gilead and McKesson specifies the roles and responsibilities of each party. Details of quality assurance and quality control measures have been described in Section 8.8.

##### **8.10.1.2. Study Discontinuation**

Gilead reserves the right to terminate the study at any time. Should this be necessary, either Gilead and/or McKesson Health Sciences will arrange discontinuation procedures and notify the appropriate regulatory agencies and institutional review boards (IRBs), where applicable.

## **9. PROTECTION OF HUMAN SUBJECTS**

This study will comply with all applicable laws, regulations, and guidance regarding patient protection including patient privacy.

As this is a retrospective observational study, there is no additional risk to participants as all data are collected from vendor EHR and patients will have no direct involvement in the study.

Confidentiality will be maintained by the assignment of a unique patient identifier to each participant. The unique patient identifier will be used on all study documentation and datasets in place of patient identifying information.

### **9.1. Good Pharmacoepidemiology and Pharmacovigilance Practices**

The study will be conducted in accordance with the International Society for Pharmacoepidemiology Guidelines for Good Pharmacoepidemiology Practices (GPP).

### **9.2. Institutional Review Board**

McKesson will submit this protocol and any accompanying material to an IRB, as applicable.

### **9.3. Informed Consent**

No informed consent will be obtained for this study. All data used in this study will be anonymized and collected in RWD vendor databases and/or an eCRF with a unique patient identifier for each patient.

### **9.4. Confidentiality**

McKesson must assure that patients' anonymity will be strictly maintained and that their identities will be protected from unauthorized parties. Only a unique identifier (as allowed by local law) and a unique study identification code should be recorded on any study-related document.

McKesson agrees that all information received from Gilead, including but not limited to this protocol, eCRFs, and any other study information, remain the sole and exclusive property of Gilead during the conduct of the study and thereafter. This information is not to be disclosed to any third party (except employees or agents directly involved in the conduct of the study or as required by law) without prior written consent from Gilead. The vendor personnel further agree to take all reasonable precautions to prevent the disclosure to any third party or otherwise into the public domain.

All parties will ensure protection of patient personal data and will not include patient names on any Gilead forms, reports, publications or in any other disclosures, except where required by laws. This study involves analysis of secondary data, and all data are anonymized to protect the privacy of patients and providers.

The retrospective research study will be conducted in accordance with legal and regulatory requirements as well as with scientific purpose, value, and rigor, and will follow generally accepted research practices. It will be necessary to obtain IRB and Compliance/Privacy approval prior to initiation of the retrospective research study data extraction and analysis. The McKesson team will submit a request for exemption, waiver of informed consent, and authorization to the IRB. McKesson will submit the appropriate documents, including but not limited to this protocol, to the McKesson Compliance/Privacy department and the IRB for review. McKesson will handle all correspondence with McKesson Compliance/Privacy and the IRB; correspondence will be kept on file at McKesson.

## **10. MANAGEMENT AND REPORTING OF SAFETY INFORMATION**

This non-interventional study is observational in nature and data are derived from electronic health records or sources where individual patient data is de-identified. Therefore, individual case safety reports are not collected or reported in an expedited fashion. Adverse events will not be solicited in this study. Safety findings from this study will be presented in aggregate in the final study report.

## **11. PLANS FOR DISSEMINATING AND COMMUNICATING STUDY RESULTS**

### **11.1. Study Report and Publications**

A non-interventional study report will be prepared.

## 13. APPENDICES

- Appendix 1. List of Stand-Alone Documents
- Appendix 2. International Working Group 2006 criteria {Cheson 2006}
- Appendix 3. Gilead Signature Page
- Appendix 4. RWD Partner Signature Page

**Appendix 1. List of Stand-Alone Documents**

| Number | Document Reference Number | Date                    | Title                       |
|---------------|----------------------------------|--------------------------------|------------------------------------|
| 1             | NDA 050794                       | Approved in 2004
by the FDA | Vidaza® US prescribing information |

FDA Food and Drug Administration

**Appendix 2. International Working Group 2006 criteria {Cheson 2006}**

**Table 13-1. 2006 International Working Group Response Criteria for Altering Natural History of MDS**

| Category                  | Response Criteria (Responses Must Last at Least 4 Weeks)  |
|---------------------------|---|
| Complete Remission        | BM: $\leq 5\%$ myeloblasts with normal maturation of all cell lines
Persistent dysplasia will be noted
Peripheral blood 
 
Hb <math>\geq 11</math> g/dL
 
Platelets <math>\geq 100 \times 10^9/L</math>
 
Neutrophils <math>\geq 1.0 \times 10^9/L</math>
 
Blasts 0%
 
   |
| Partial Remission         | All CR criteria if abnormal before treatment except:
BM blasts decreased by $\geq 50\%$ over pretreatment but still $> 5\%$
Cellularity and morphology not relevant   |
| Marrow CR                 | BM: $\leq 5\%$ myeloblasts and decrease by $\geq 50\%$ over pretreatment
Peripheral blood: if HI responses, they will be noted in addition to marrow CR  |
| Hematological Improvement | Please refer to Table 13-2 below  |
| Stable Disease            | Failure to achieve at least PR, but no evidence of progression for $> 8$ weeks  |
| Failure                   | Death during treatment or disease progression characterized by worsening of cytopenias, increase in percentage of BM blasts, or progression to a more advanced MDS FAB subtype than pretreatment  |
| Relapse After CR or PR    | At least 1 of the following: 
 
Return to pretreatment BM blast percentage
 
Decrement of <math>\geq 50\%</math> from maximum remission/response levels in granulocytes or platelets
 
Reduction in Hb concentration by <math>\geq 1.5</math> g/dL or transfusion dependence
 
   |
| Cytogenetic Response      | Complete 
 
Disappearance of the chromosomal abnormality without appearance of new ones
 
 Partial 
 
At least 50% reduction of the chromosomal abnormality
 
  |
| Disease Progression       | For patients with: 
 
Less than 5% BM blasts: <math>\geq 50\%</math> increase in blasts to <math>> 5\%</math> blasts
 
5%-10% BM blasts: <math>\geq 50\%</math> increase to <math>> 10\%</math> blasts
 
10%-20% BM blasts: <math>\geq 50\%</math> increase to <math>> 20\%</math> blasts
 
20%-30% BM blasts: <math>\geq 50\%</math> increase to <math>> 30\%</math> blasts
 
 Any of the following: 
 
At least 50% decrement from maximum remission/response in granulocytes or platelets
 
Reduction in Hb by <math>\geq 2</math> g/dL
 
Transfusion dependence
 
 |

| Category | Response Criteria (Responses Must Last at Least 4 Weeks)  |
|----------|---|
| Survival | Endpoints: 
 
• Overall: death from any cause
 
• Event free: failure or death from any cause
 
• PFS: disease progression or death from MDS
 
• DFS: time to relapse
 
• Cause-specific death: death related to MDS
 
 |

BM bone marrow; CR complete remission; DFS disease free survival; FAB French American British; Hb hemoglobin; HI hematologic improvement; MDS myelodysplastic syndrome; PR partial remission

